1 PROTOCOL SUMMARY

1.1 SYNOPSIS

Title:

Grant Number:

Study Description:

OA Clinic-Community CARE Model (*OA CARE*)

1 R21 AR080309-01

The overall objective of this study is to conduct a randomized pilot trial of *OA CARE* among n=60 patients with knee and/or hip osteoarthritis (OA) and overweight / obesity who are not currently meeting physical activity recommendations. Participants will be randomly assigned to *OA CARE* or a usual care (UC) group. Assessments will be conducted at baseline, 6 months and 12 months.

Objectives*:

Specific Aim 1: Assess the feasibility and acceptability of *OA CARE*. Feasibility metrics will include recruitment rate, completion rates for weight loss and exercise program visits, referrals to and utilization of services noted above and proportion of participants completing follow-up assessments. Acceptability of *OA CARE* will be evaluated from both patient and Primary Care Provider (PCP) perspectives.

Specific Aim 2: Obtain preliminary data on the efficacy of *OA CARE* with respect to the primary outcome of change in total Western Ontario and McMaster Universities Osteoarthritis Index (WOMAC) score. The WOMAC will be administered at baseline, 6-months and 12-months, along with secondary outcomes including body weight, physical activity, physical function, sleep measures and psychological measures. We will also collect preliminary data on costs of *OA CARE*.

Endpoints*:

Primary Endpoint:

WOMAC Total Score. This will be assessed at baseline and 6-month and 12-month follow-up time points.

Secondary Endpoints: Objectively assessed physical activity (PA), measured via accelerometer, body weight, and objective assessments of physical function; WOMAC self-reported pain and function. These will be assessed at baseline and 6-month and 12-month follow-up time points.

Exploratory Endpoints: self-reported sleep and psychological measures, balance, and preliminary data on costs of *OA CARE*

Feasibility and acceptability metrics include recruitment, retention, intervention delivery, and outcome assessment. Perceptions of acceptability will be obtained from patients and providers using open-ended questions.

Study Population:

N = 60 participants with knee and/or hip osteoarthritis (OA) and overweight / obesity who are not currently meeting physical activity recommendations. We will enroll both males and females from all racial and ethnic backgrounds.

Phase* or Stage:

Exploratory pilot trial

Description of Sites/Facilities Enrolling Participants:

We will recruit patients from UNC Health. In particular, we will partner with the UNC Internal Medicine Clinic and UNC Family Medicine.

Description of Study Intervention/Experimental Manipulation:

OA CARE includes evidence-based behavioral weight management and exercise interventions, as well as tailored referrals to physical therapy, psychological interventions, additional weight / nutrition-related services and sleep-related services based on patient-specific needs and in coordination with the PCP.

[figure not shown]
Study Duration*:

2 years

Participant Duration:

12 months

1.2 SCHEMA

1.3 SCHEDULE OF ACTIVITIES

		Pre-screening (Pre-consent)	Visit 1 Day 1	Visit 2 Day 11 to 25	Visit 3 (1 to 2 weeks after Visit 2)	Visit 4 (1 to 2 weeks after Visit 3)	Visit 5 (5-6 months after Visit 2)	Visit 6 (OA CARE 6 Months after Visit 2; Usual Care 6-months after Visit 2)	Visit 7 (OA CARE 12-months after Visit 2; Usual Care 12-months after Visit 2)
EMR Review Eligibility	X								
Screening Phone Call									
Informed Consent & HIPAA	X								
Outcome Measures									
Objectively Assessed Physical Activity (accelerometer)	X						X	X	X
Patient Reported Measures:									
-Physical Function (WOMAC)	X						X	X	X
-Pain (WOMAC)	X						X	X	X
-Sleep (STOP Questionnaire and Insomnia Severity Index)						X	X	X	X
-Psychological Measures (Patient Health Questionnaire-8, Pain Catastrophizing Scale and Arthritis Self-Efficacy Scale)						X	X	X	X
-Modified version of the Community Health Activities Model Program for Seniors (CHAMPS) Physical Activity Measure	X					X	X	X	X
BMI measure							X	X	X
Physical Performance Measures:							X	X	X
-30-second stair stand test	X						X	X	X
-Timed up-and-go test	X						X	X	X
-2-minute march test	X						X	X	X
-Single Leg Stance Test	X						X	X	X
Participant Characteristics	X						X	X	X
Acceptability							X	X	X
Randomization		X							
Control & Experimental Interventions:									
-OA CARE			X	X	X	X	X	X	X
-Usual Care Control			X	X	X	X	X	X	X
Adverse Event Reporting			X	X	X	X	X	X	X

2 INTRODUCTION

2.1 STUDY RATIONALE AND BACKGROUND

2.1.1. CLINICAL SIGNIFICANCE

Osteoarthritis (OA) is a Significant Burden for Individuals and Health Care Systems. OA affects over 32 million U.S. adults (1 in 7) and is a leading cause of pain and disability¹. OA also has substantial impacts on work participation, mental health, sleep, development of other chronic conditions and even mortality². Already associated with significant health care utilization and costs, the prevalence of OA is expected to rise substantially in coming decades¹. This will place increasing demands on health care systems, highlighting the importance of developing and implementing efficient models that ensure a high quality of care for patients.

There are Persistent Deficiencies in Quality of Care for OA. Multiple studies have highlighted discordance between guideline-based OA care and actual clinical practice³⁻⁷. Despite agreement across OA treatment guidelines regarding the effectiveness and centrality of lifestyle (e.g., weight management, physical activity) and rehabilitation therapies⁸, pass rates for quality indicators related to these therapies are only about 40%⁴. Data from primary care visits involving treatment for OA in the U.S. show that <50 out of 1000 addressed physical therapy as a potential treatment, and only about 250 out of 1000 addressed core lifestyle components⁹. Other studies have also documented low use of and recommendations for behavioral and rehabilitative therapies^{3,5-7}. For example, in analyses of patients with knee OA across 3 different U.S. health systems, only 40-50% of patients had ever received physical therapy for this condition⁵. *These gaps in care are highly problematic, as they fail to engage patients with evidence-based treatments that are known to improve key outcomes including pain, disability, mental health and even disease progression¹⁰⁻¹³.*

Evidence-Based Care Models are Needed to Improve OA Care Quality in the US. In response to the well-established deficiencies in care quality for knee and hip OA, there has been increasing interest in the development of systematic OA care models internationally¹⁴⁻¹⁷. Care models are defined as organized, planned approaches to improving health, focusing on particular patient populations (e.g., individuals with OA) to ensure that every patient receives optimal medical care¹⁸. Although there have been several randomized controlled trials (RCTs) of OA care models^{14,15,19}, there are three major limitations with respect to how this research can inform care for OA in the U.S. First, there have been no RCTs of OA care models in the U.S., and models developed in other countries are not designed to fit the organizational structures or payment models of U.S. healthcare systems. Second, the effectiveness of previously studied OA care models has been limited; we believe a key weakness has been the lack of robust incorporation of lifestyle components, particularly weight loss^{15,19}. Third, prior models have been limited in terms of reach and sustainability because of significant requirements for busy health care providers^{14,15,17,19}. *OA CARE will address each of these challenges, building an efficient, scalable model that is designed for sustainability and adequately addresses all components of guideline-concordant care.* This exploratory trial will accomplish key steps toward the first RCT of an OA care model in the U.S.

2.1.2. SCIENTIFIC RATIONALE

The OA CARE model incorporates the following 4 key principles and evidence from the scientific literature:

- 1) In alignment with OA treatment guidelines,^{8,10,20} OA CARE takes a multifactorial approach that includes both pharmacological and non-pharmacological components.
- 2) OA CARE emphasizes delivery of lifestyle interventions, which are considered first-line treatments, appropriate for all patients with hip and knee OA^{8,10,20}.
- 3) OA CARE involves a stepped care approach, in which patients begin with first-line interventions (weight management and physical activity) and then advance to additional therapies as needed.²¹ A stepped care approach is efficient, patient-centered and supported by multiple studies, including our recent trial of a STepped Exercise Program for Knee Osteoarthritis (STEP-KOA).^{21,22}
- 4) OA CARE will involve an innovative partnership with the YMCA to deliver weight management and exercise programs. The Centers for Disease Control and Prevention, Institute of Medicine and other organizations have recommended and prioritized clinic-community partnerships based on evidence for effectiveness²³. These partnerships address the problems of limited time in clinical visits and the large number of patients who need these types of services.

2.1.3. PRIOR STUDIES AND RATIONALE FOR DEVELOPMENT

This study builds on our team's successful trials, programs and collaborations, including the following:

- We have collectively conducted over a dozen trials of behavioral interventions that support the evidence base for weight management, exercise, physical therapy, psychological and multi-component interventions as effective treatments for knee and hip OA^{22,24-37}. These trials have given our team ample experience in patient recruitment, behavioral intervention delivery and fidelity monitoring, outcome assessment, and robust statistical analyses. We also have experience in delivering interventions involving PCPs and the use of algorithms to guide patient referrals to specific OA treatments^{29,30}.
- The Osteoarthritis Action Alliance (OAAA), a key partner ([name], Director), is a national coalition of over 130 organizations with a mission of reducing the public health burden of OA. The OAAA has experience in working with the YMCA (one of their member organizations) and other community organizations to deliver evidence-based lifestyle interventions, has developed stakeholder-informed patient and provider OA educational tools, and is engaged with vast network of partner organizations that will be instrumental in future implementation of *OA CARE*.
- *OA CARE* has been developed in partnership with key stakeholders. At the outset of developing this care model, we convened a group of clinicians and clinic administrators representing Internal Medicine, Family Medicine, Orthopedics, Physical Therapy and Rheumatology. *OA CARE* is based on this group's input regarding current gaps in care and processes that would be feasible and sustainable for clinics and providers. We also received input from on the project from our Thurston Arthritis Research Center Patient Stakeholder Advisory Board; they emphasized the importance of including rural patients and suggested that for patients who receive physical therapy during the study, we aim to integrate this with exercise opportunities at the YMCA, since this could enhance the benefits of physical therapy visits and augment integration of *OA CARE* components. We will engage with these stakeholder groups throughout all phases of this research program.
- The YMCA is currently engaged in clinic-community partnership efforts of direct relevance to this study. In particular, our local partners at the Triangle YMCA are currently funded by Blue Cross Blue Shield to conduct a 5-year project focused on referrals of patients from health systems to YMCA Medical Memberships, which include access to a variety of group programs plus health coaching. Their project aims to evaluate YMCA Medical Memberships as a population health approach and potential coverage as a health benefit; these goals are directly aligned with our plans for implementing and evaluating *OA CARE*. In addition, the Triangle YMCA has set up processes for sharing patients' outcome data with their PCPs through the electronic health record (EHR). The Triangle YMCA has been very successful during their first year of this project, enrolling >700 patients from 7 major health systems including University of North Carolina (UNC) Health.

2.2 RISK/BENEFIT ASSESSMENT

2.2.1 KNOWN POTENTIAL RISKS

Emotional distress: it is unlikely that the types of questions participants will be asked in this study will result in emotional distress, but we understand that participants may be uncomfortable with answering questions about some aspect of their health or other things about them. To minimize this risk, we will let participants

know they may choose not to answer any study questions and can still be involved in the study. Additionally, participants in the *OA CARE* intervention will have contact information for the study team (e.g. *OA CARE* Navigator) and a YMCA health coach to discuss any concerns.

Breach of confidentiality: we will be collecting some elements of personal health information necessary for the study. To minimize breaches of confidentiality, all data will be stored on a secure UNC server or a UNC IRB approved platform for sharing PHI (with YMCA) and paper information will be stored in locked filing cabinets in the office of a study team member, and only approved study personnel will have access to those data.

Personal health information (e.g. patient name and contact information only) will be shared with YMCA health coaches and personnel conducting the YMCA weight loss and exercise programs. Any information shared between approved UNC study team members and YMCA personnel will be done verbally by phone, by encrypted email or a UNC IRB approved platform for sharing PHI.

For participants in the *OA CARE* intervention, personal health information (e.g. patient name and DOB or MRN) will be shared with the participant's PCP, as part of the brief progress reports sent by the *OA CARE* Navigator. Any information shared between approved UNC study team members (e.g. *OA CARE* Navigator) and the participant's PCP will be done by encrypted email or UNC IRB approved platform for sharing PHI.

Risks of Exercise: Participants in the *OA CARE* intervention will be involved in physical activity programming at the YMCA. This will be tailored to individuals with knee OA. However, exercise programs may be associated with risk of injury, muscle soreness, and joint pain. The risk of sudden death during physical activity is about 1 death per 656,000 hours of physical activity. In general, the risk of these events with moderate physical activity is very low.

Risks of weight loss interventions: Participants in the *OA CARE* intervention will be involved in a weight management program at the YMCA. Side effects associated with weight loss in general may be hair loss, fatigue, weakness, gall bladder disease, and electrolyte abnormalities. Also, low blood sugar or low blood pressure (lightheaded or fainting) may occur during weight loss if a participant is taking medications for diabetes or high blood pressure. These risks are not specific to this research but also apply to usual care.

2.2.2 KNOWN POTENTIAL BENEFITS

Participants may experience improvements in pain, physical function or other symptoms related to OA, from participating in the *OA Care* program. It is possible that this study may not benefit participants directly, but participation in this study may lead to information that can benefit other patients with knee and/or hip OA, as well as their health care providers.

2.2.3 ASSESSMENT OF POTENTIAL RISKS AND BENEFITS

This is a minimal risk study with physical risks that are comparable to those that would be encountered with exercise programs in clinical or community settings. Furthermore, we do not anticipate any significant psychological, social, financial, or legal risks to be associated with participation in this study. Given the high and increasing rate of OA, the persistent deficits of physical inactivity, and the lack of a standard, evidence-based approach to address these deficits in primary care settings, we believe the value of the information to be gained outweighs the risks of participation in the study.

3 STUDY OBJECTIVES AND ENDPOINTS

OBJECTIVES	ENDPOINTS	JUSTIFICATION FOR ENDPOINTS
Primary		
Assess the feasibility and acceptability of OA CARE	
Feasibility metrics will include recruitment rate, completion rates for weight loss and exercise program visits, referrals to and utilization of services noted above and proportion of participants completing follow-up assessments.
 
Acceptability of OA CARE will be evaluated from both patient and PCP perspectives. PCP perspectives and recommendations will be conducted as a stakeholder engagement activity; PCPs will not be considered research participants.
	These metrics are essential for assessing the feasibility of conducting a larger scale trial of OA CARE.
Obtain preliminary data on the efficacy of OA CARE with respect to the primary outcome of change in total Western Ontario and McMaster Universities Osteoarthritis Index (WOMAC) score.	Western Ontario and McMaster Universities Osteoarthritis Index (WOMAC) pain, stiffness, and function subscales, assessed at baseline, 6 months and 12 months. We will separately examine WOMAC pain and function subscales as secondary outcomes.	This primary metric will be assessed because it is a key outcome in OA and can be improved with regular PA. The 12-month time point corresponds to the end of the OA CARE intervention, and the 6-month time point will allow assessment of the time course of changes in outcomes.
Secondary		
Obtain data on the efficacy of the OA CARE program with respect to improvement in body weight, physical activity and physical function.	
Physical activity will be accessed via accelerometer. Moderate to vigorous physical activity (MVPA; primary metric), light intensity activity, sedentary minutes, step counts and other PA metrics, assessed at baseline, 6 months and 12 months.
 
Physical Function tests: 30-second chair stand test, timed up-and-go test, 2-minute march test and single
	These secondary metrics will be assessed because they are also key outcomes in OA, and they map onto the different components of the OA CARE intervention. The 12-month time point corresponds to the end of the OA-CARE intervention, and the 6-month time point will allow assessment of the time courses of changes in outcomes.

OBJECTIVES	ENDPOINTS	JUSTIFICATION FOR ENDPOINTS
	
leg stance assessed at baseline and 12 months.
 
Body Weight will be assessed using a research / clinical grade scale.
 
Participants' height will also be measured to calculate body mass index (BMI).
	
Tertiary / Exploratory		
Obtain data on the efficacy of the OA CARE program with respect to the change in exploratory outcomes.	
Exploratory outcomes include psychological measures (Patient Health Questionnaire-8, Pain Catastrophizing Scale and Arthritis Self-Efficacy Scale) assessed at baseline, 6 months and 12 months. We will collect self-reported sleep measures (STOP Questionnaire and Insomnia Severity Index) for the OA CARE intervention. We will also collect preliminary data on costs of OA CARE.
	
These outcomes are also important for patients with knee OA and map onto OA CARE intervention components. The 12-month time point corresponds to the end of the OA-CARE intervention, and the 6-month time point will allow assessment of the time courses of changes in outcomes.

4 STUDY DESIGN

4.1 OVERALL DESIGN

The aim of this study is to conduct an exploratory randomized controlled trial with 60 patients with knee and / or hip OA equally randomized to *OA CARE* or a usual care (UC) control group (Figure 1) . Sub-aims are as follows:

Aim 1. Assess the feasibility and acceptability of OA CARE. Feasibility metrics will include recruitment rate, completion rates for weight loss and exercise program visits, referrals to and utilization of services noted above and proportion of participants completing follow-up assessments. Acceptability of OA CARE will be evaluated from both patient and PCP perspectives.

Aim 2. Obtain preliminary data on the efficacy of OA CARE with respect to the primary outcome of change in total Western Ontario and McMaster Universities Osteoarthritis Index (WOMAC) score. The WOMAC will be administered at baseline, 6-months and 12-months, along with secondary outcomes including body weight, physical activity, physical function (baseline and 12 months only), sleep measures and psychological measures. We will also collect preliminary data on costs of OA CARE.

This will be an exploratory RCT with 60 patients equally randomized to OA CARE or a usual care (UC) control group (Figure 1); randomization will be in block sizes of 20. Assessments will occur at baseline, 6-month follow-up and 12-month follow-up. The UC group will be offered a 12-month YMCA Medical Membership (described below) once they have completed follow-up assessments.

[figure not shown]

Figure 1. Study Design

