5.5. STRATEGIES FOR RECRUITMENT AND RETENTION

We will recruit patients from UNC Health. In particular, we will partner with the UNC Internal Medicine Clinic and UNC Family Medicine, which serves high proportions of patients who are African American and non-white Hispanic, as well as uninsured patients. This is important because of disparities in OA among these demographic groups⁴⁵, and our aim for *OA CARE* to particularly reach the most vulnerable patients. Our team has a strong track record of recruiting African American and non-White Hispanic patients^{28,31,46}. Our main recruitment method will mirror the process by which we envision *OA CARE* will ultimately function in clinical settings. Specifically, PCPs will be asked to refer patients to *OA CARE*. This may occur via the EHR or another UNC approved method of transferring PHI. A study team member will then screen the EHR for potential exclusion criteria and contact the patient to assess interest and administer a brief screening questionnaire. If needed, we will also identify potential participants via an EHR data pull, then send introductory letters and follow up with a screening phone call. However, a key goal for this exploratory study is to develop procedures to maximize provider referrals, as this will be critical for downstream implementation. All eligible patients will be asked to attend a baseline visit that will involve completion of consent, baseline assessments and receipt of an accelerometer. Following return of the accelerometer, participants will be informed of their randomization assignment via telephone. A participant will be considered enrolled once they have consented and been randomized.

To facilitate completion of recruitment calls, as well as baseline and follow-up assessment calls, we will call participants on different times of day and different days, across multiple weeks. We have used this strategy successfully in prior studies to reach participants at times convenient to them.

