Weight Loss & Exercise Interventions. Evidence-based weight loss and exercise programs will be delivered by the Triangle YMCA, within the structure of the Medical Membership. (All services provided to study participants by the YMCA will be their standard programming; they will note be delivering a study-specific intervention.) This membership provides access to multiple group exercise programs, exercise facilities, and a health coach who assists members with meeting health goals and selecting appropriate programs and classes. All patients in OA CARE will begin with participation in the YMCA’s Weight Loss Program (Program). This program involves 12 weekly sessions that include goal-setting, food and activity tracking, introduction to physical activity offerings, and weigh-ins. This Program is based on best practices from evidence-based behavioral weight loss programs. Participants may repeat the program following the first 12-week session if they have not met weight loss goals and / or would like continued structure and support for these behavior changes. The Triangle YMCA will deliver the Weight Loss Program to OA CARE members in groups of approximately 10; this will provide cohesion for OA CARE participants. In the beginning of the study, the Program will be delivered virtually (e.g. video conferencing platform) for feasibility reasons (e.g., potential for study participants to reside in different geographic locations that would make travel to a central location challenging). However, the Program may be offered in-person in the future. During the screening call, we will assess whether the patient has internet access and a device (computer, tablet, smartphone) on which they can access the Program. If the patient screens ineligible for this reason, we will ask the patient if they would like to be contacted, if the Program is offered in-person at a future date. If we do offer the Program in person, this will no longer be considered an exclusion criterion. The YMCA offers many exercise programs and classes appropriate for individuals with OA. A YMCA health coach will assist participants with selecting an exercise program (including appropriateness based on their pain and functional limitations) and continuing to engage with exercise-based therapies throughout their 12-month involvement in OA CARE. The UNC study team will also give participants instructions regarding how to access a free Walk With Ease workbook (through the OAAA’s online portal) and take advantage of other tools available through this program.

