6.3 MEASURES TO MINIMIZE BIAS: RANDOMIZATION AND BLINDING

The randomization scheme will be generated by the study statistician and stored within the study database. The database will be configured so that blinded study personnel (e.g., those conducting follow-up assessments) will not have access to randomization information. The participants will not be notified of randomization assignment until all baseline assessments are complete. In addition, an individual participant's randomization assignment will not be known to any study personnel until baseline assessments are complete.

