6.4 STUDY INTERVENTION ADHERENCE

The study database will be used to track participants' completion of all assessment visits, as well as all contacts with the *OA CARE* Navigator. The coordinator will also maintain close communication with the *OA CARE* Navigator regarding facilitation of all activities within the care pathway. The YMCA will provide documentation of patients' participation in specific YMCA programs to the *OA CARE* Navigator; this information will also be summarized for PCPs. Also, for each patient, the *OA CARE* Navigator will maintain a checklist of intervention activities, target dates, dates of completion, and comments.

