7.2 PARTICIPANT DISCONTINUATION/WITHDRAWAL FROM THE STUDY

Participants are free to withdraw from participation in the study at any time upon request. An investigator may discontinue a participant from the study for the following reasons:

- Lost-to-follow up; unable to contact subject
- Any event or medical condition or situation occurs such that continued collection of follow-up study data would not be in the best interest of the participant or might require an additional treatment that would confound the interpretation of the study
- The participant meets an exclusion criterion (either newly developed or not previously recognized) that precludes further study participation

The reason for participant discontinuation or withdrawal from the study will be recorded in the study database. Participants who discontinue or are withdrawn will be replaced up to the point of randomization assignment being given to the participant. Once participants are given their randomization assignment, they will be counted toward the total study sample size and not replaced.

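### A single printed block size of 20 lets unblinded staff deduce some end-of-block assignments, so the concealment stated in Section 6.3 is not fully protected; the likely bias is small and the remedy is cheap

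*Combined protocol and SAP*

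**What the plan says.** Section 4.1 plans for "60 patients equally randomized to OA CARE or a usual care (UC) control group" and states that "randomization will be in block sizes of 20". No stratification and no variation in block size is described.

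Section 6.3 has the statistician generate the scheme and store it in the study database. It gives two protections. The first is restricted access: "blinded study personnel (e.g., those conducting follow-up assessments) will not have access to randomization information". The second is a general assurance that an individual's "randomization assignment will not be known to any study personnel until baseline assessments are complete".

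Section 5.5 describes release: "Following return of the accelerometer, participants will be informed of their randomization assignment via telephone". Under Section 7.2, participants who have been given an assignment stay in the count: "they will be counted toward the total study sample size and not replaced". Section 6.1 has the YMCA deliver the weight-loss program to "OA CARE members in groups of approximately 10", which is half of a block of 20. Section 6.4 adds, of the OA CARE Navigator: "The coordinator will also maintain close communication with the" Navigator about the care pathway. Section 8.1 says that the baseline, 6-month and 12-month measures are collected by a team member who is blinded to assignment.

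**The concern.** Restricting database access stops staff from looking assignments up. It does not stop someone who already knows the past assignments from working out the next one. The Navigator schedules OA CARE patients, and someone telephones the assignments, so at least these people see the sequence unfold. Because assigned participants are not replaced, a running tally stays valid. Because the block size is fixed and printed, the tally shows when one arm's ten places are used up, and every remaining assignment in that block is then known.

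Advance knowledge matters where judgement enters before assignment. Section 5.2 includes an exclusion left to the study team's determination, Section 5.5 allows repeated recruitment calls over several weeks, and Section 7.2 allows replacement until the assignment is given. The documents do not say whether the people who screen, consent or schedule are blinded. At stake is the comparability of two arms of 30, whose difference Section 9.4 uses to help size the next trial.

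**Working it through.** The plan gives no predictability figure, so there is none to reproduce.

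**Inputs.** 60 participants, 1:1, in blocks of 20 (Section 4.1). This gives 60/20 = 3 blocks, each with m = 10 places per arm. Release is taken to be one participant at a time (Section 5.5).

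**Assignments known with certainty, nobody pending.** Let R be the number of assignments left in a block when one arm fills.

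- P(R = r) = 2·C(19−r, 9)/C(20, 10). For example, P(R = 1) = 2·48,620/184,756 = 0.526, so P(R ≥ 2) = 0.474.
- E[R] = 2m/(m+1) = 20/11 = 1.82 per block.
- Three blocks: 3 × 1.82 = 5.45 of 60 (9.1%), SD 1.9. Simulation of 20,000 blocks gives 5.49.
- The minimum is 3, because the last place in each block is always forced.

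**Allowing for a queue.** If k earlier participants have not yet been assigned when the prediction is made, the tally lags by k, and the expected number known is 3·E[max(R − k, 0)].

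| k pending | expected known, of 60 |
|---|---|
| 0 | 5.45 |
| 1 | 2.45 |
| 2 | 1.03 |
| 3 | 0.40 |
| 4 | 0.14 |

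**Which row applies at the baseline visit.** The documents do not give an accrual rate, so this step rests on assumptions. A 2-year study with 12 months per participant (Section 1.1) leaves at most about 12 months to enrol. Section 1.3 puts Visit 2 at Day 11 to 25; take the gap from baseline visit to assignment as 10 to 24 days. Even accrual over 52 weeks then gives 60/364 × 10 = 1.6 to 60/364 × 24 = 4.0 participants pending. Accrual over 39 weeks gives 2.2 to 5.3, and over 26 weeks 3.3 to 7.9. The lower rows of the table are therefore the relevant ones at consent, and more so at screening, which is earlier.

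**Other block schemes.**

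- Shorter fixed blocks are worse. The formula gives 6 × 10/6 = 10.0 certain assignments for blocks of 10, 10 × 6/4 = 15.0 for blocks of 6, and 15 × 4/3 = 20.0 for blocks of 4.
- Blocks of 16, 20 and 24 in random order total 60, with 8 + 10 + 12 = 30 per arm. If staff know these three sizes but not their order, simulation gives about 2.6 certain assignments of 60 with nobody pending.
- Guessing the arm with more places left is right about 62% of the time (about 37 of 60) under fixed blocks of 20, and also about 62% under 16/20/24.

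**The case against.** The strongest reply is about timing. The average of 5.5 applies only immediately before release at accelerometer return, when consent and the in-person baseline are over and little discretion remains apart from delay or a pre-assignment withdrawal. The discretionary steps come earlier, when others are probably pending and far fewer assignments can be deduced. This stands. A reader might infer from the 5.5 that about one enrolment decision in eleven could be made with knowledge of the arm; the documents do not support that.

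It is also fair that Sections 6.3 and 8.1 together already keep assignments from those who collect baseline measures, and that the Navigator's listed duties in Section 6.1 include neither screening nor consent. What remains is silence about screeners, schedulers and any consenter who is a different person. Silence is a gap to close, not evidence that unblinded staff do this work.

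Section 6.3 can also be read as a statement about access rather than inference. Any scheme that ends at exactly 30:30 forces the last assignment, including the one proposed here. So the claim is that the assurance is not fully protected, not that it is plainly false.

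Finally, Section 4.2 says the trial is not powered for efficacy, Section 9.4 adjusts for baseline WOMAC, and 20 is already a long block. These points limit the consequence. They do not explain why the size must be fixed and printed.

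**Conclusion.** The point holds as a minor one. With one fixed, disclosed block size, an unblinded person who tallies both arms can deduce at least 3 and on average 5.5 of 60 assignments just before release, and about 2.5 to 0.14 when 1 to 4 earlier participants are pending. This assumes release one at a time and a complete tally. If each block were randomized as a batch after all 20 baselines, the problem would vanish, but the documents do not describe that.

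Two stronger readings should be avoided. The first is that selective enrolment is likely or that baseline balance is compromised: nothing in the documents shows this, and the expected bias is small. The second is that the 62% guessing rate, against 50% by chance, is caused by printing the block size. That guess needs only the running imbalance, and varying the block sizes leaves it unchanged.

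**What to change.** Have the statistician generate the list with varied block sizes in random order, for example 16, 20 and 24, giving OA CARE groups of 8, 10 and 12. Remove the block size from Section 4.1 and hold it in a file that only the statistician can open. Do not shorten the fixed block instead. The gain to claim is fewer certain assignments (about 2.6 of 60 instead of 5.5, both with nobody pending), even if the set of sizes leaks. Lower guessing accuracy should not be claimed.

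If the current list is already in use, leave it and extend the access restriction in Section 6.3: staff who screen, consent and schedule cannot see earlier assignments.

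The cost is a new list and a wording change in the first case, and one sentence in the second. The only practical downside is YMCA groups of 8 to 12 rather than exactly 10, which is close to the approximate size that Section 6.1 gives.
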